#### **Reporting and Follow-up of Misuse and Overdose**

Drug misuse and drug overdose should always be reported in the same format (i.e., on SAE form) and within the same timelines as a SAE, even if they may not result in an adverse outcome.

When an “overdose” or “drug misuse” of the trial vaccine occurs without an AE, the Investigator should also complete an “SAE/AESI/overdose/misuse report form” and send this to the Sponsor’s safety contact.

It should be clearly stated that no AE was observed. If no SAE is associated, misuse/overdose will be assessed as non-serious.

In this case, there is no need to complete the “Averse Event” screen in the eCRF.

#### **Product Quality Complaints**

Pharmaceutical Technical Complaints associated with the trial vaccine must be reported to the Sponsor immediately (refer to the pharmacy manual for details).

The same reporting timelines as for SAEs apply.

## Appendix 11 Protocol Amendment History

The trial was initiated using protocol version 1.0.

### ***Protocol version 2.0: 19 March 2021***

Section # and Name	Description of Important Change	Brief Rationale
Throughout	Changed “students in clinical years” for “students in clinical training”.	Clarification
Throughout	Subjects who report to have COVID-19 symptoms will only be followed-up if the Investigator considers the symptoms could potentially indicate a COVID-19 case.	Clarification
Throughout	Subjects who tested positive for SARS-CoV-2 outside of the trial context (RT-PCR) are to be considered for active surveillance for COVID-19 (see Appendix 6).	Completeness
Throughout	Unblinding will be allowed in the case a subject becomes eligible to receive an authorized/licensed vaccine.	Several vaccine candidates have been approved for emergency use since the original protocol
Synopsis	Inclusion of information on authorized vaccine availability.	Update
Synopsis and 6.2 Exclusion Criteria	History of pIMD separated from history of angioedema or anaphylactic reaction.	Clarification
Synopsis, 9.2.1.1.1 Routine Surveillance for COVID-19, and 9.5.1 Virological Confirmation of COVID-19 Disease	Instructions added to state that viral RNA of SARS-CoV-2 should be sequenced at a Sponsor-designated laboratory to identify S protein variants in subjects with positive RT-PCR tests.	To identify mutations in this protein

Section # and Name	Description of Important Change	Brief Rationale
5.1 Overall Design and 6.3 Vaccine Delay Recommendations	Guidance added that subjects may receive the second trial vaccine dose if they develop COVID-19 between the first and second doses (after being symptom-free for 2 weeks).	Clarification
9.3.3 Adverse Events	Inclusion of instructions that COVID-19 illness and its complications/sequelae are to be reported as an AESI, according to Appendix 9.	Clarification
9.3.6 Vital Signs and Physical Examination	Exclusion of the genitourinary system examination from the complete physical examination. Inclusion of O 2 saturation measurement at the discretion of the investigator.	Correction
Throughout	Minor editorial and document formatting revisions.	-

**Protocol Version 3.0: 23 July 2021**

Section # and Name	Description of Important Change	Brief Rationale

1 Synopsis, 2 Schedule of activities, 3.2.3 Assessment of potential risk and benefits, 4.2.3 Exploratory endpoints, 7.3.3.2 Authorized/ licensed vaccine, 7.6.2 Prohibited medications/ vaccines during the Trial, and 9.1 Schedule of Trial assessments and procedures
	
Introduced the summary of CVnCoV final efficacy analysis of the HERALD trial and, following that, the unblinding of all blinded subject and subsequent change on the schedules of activities to guarantee safety follow up of all the subjects exposed to CVnCoV and access to information on the HERALD final analysis results for all the subjects.
	
Update following availability of the final efficacy analysis results of the HERALD trial.

**Protocol Version 4.0: 11 August 2021**

Section # and Name	Description of Important Change	Brief Rationale
1 Synopsis and 3.2.3 Assessment of potential risk and benefits	Clarification that the Study Physician will be responsible for providing study results to subjects.	Clarification
9.4.3 Antibody Responses to CVnCoV Vaccination in Subjects Who Develop a Case of COVID-19	Subjects receiving authorized SARS-CoV-2 vaccines will not be included in the antibody response.  See Table 2	Clarification
Throughout	Minor editorial and document formatting revisions.	-

**Protocol Version 5.0: 22 December 2021**

Section # and Name	Description of Important Change	Brief Rationale
Protocol Approval Signatures	New Medical Responsible Person [REDACTED]	Change of responsibility
SAE Hotline and Medical Monitor Contact	Added e-mail address for post-trial safety reporting	Change of safety reporting e-mail address after end of trial
Synopsis	Trial will remain blinded until approval of study protocol version 3.0.	Clarification

Synopsis / Schedule of Trial Assessments Table 1, 2 and 3
 
3.1.4 Trial Rationale
 
4.1.2 Secondary Endpoints
 
4.2 Endpoints
 
4.3 Estimands
 
5.1 Overall Design
 
5.2 Scientific Rationale for Trial Design
 
9.1.1.10; 9.1.2.7 End of Trial Visit
 
9.2.1.1.1 Routine Surveillance for COVID-19
 
9.4 Immunogenicity Assessments
 
10 Statistical Considerations
	
Assessment of cell mediated immune (CMI) response cancelled.
 
Comparison of efficacy by pooling of results with study COVID19-5-P-002 cancelled.
 
Limitation of immunogenicity analyses to 100 CVnCoV subjects per lot and 50 placebo subjects and to the following time points: Baseline, Day 29 and Day 43.
 
Assessment of seroconversion to the N-protein of SARS-CoV-2 at Day 393 cancelled.
 
Assessment of efficacy of CVnCoV in the prevention or reduction of asymptomatic infections cancelled.
	
Analyses no longer required.

	
Measurement of antibody responses for all Covid-19 cases that occur in the trial cancelled.
 
For positive RT-PCR tests, viral RNA of the SARS-CoV-2 sequencing to identify S protein variants no longer required.
	

1. Synopsis
 
5.1 Overall Design
 
9.2.1.3 COVID-19 Case Definition for the Efficacy Analysis
 
9.2.1.4 Adjudication of COVID-19 Cases
 
9.3.8.2 Adjudication Committee
	
Efficacy cases must no longer be confirmed by adjudication
	
Confirmation no longer required

9.3.3.2 Safety Assessments for All Subjects
 
Appendix 12 Adverse Events: Definitions and Procedures for Recording, Evaluating, Follow-up, and Reporting
	
AE recording only to be done for criteria defined in section 9.3.2
	
Clarification

8 Discontinuation / Withdrawal Criteria
	
Withdrawal procedure for placebo subjects added
	
Clarification


11.3 Monitoring
	
Option for remote source data verification included
	
Implementation of Guidance on the Management of Clinical Trials during the Covid-19 (Coronavirus) Pandemic

2.0 Change History

Version/Date	Change Log
0.1	Draft Version of the SAP
1.0 / 14 Jan 2021	Final Version of the SAP
1.1 / 21 Apr 2021	Updates: 
 • Minor modifications to Section 6.1 to clarify the main censoring rules following unblinding • Clarification on data handling for subjects who have been tested positive for COVID-19 in Section 9.5.4 • Addition of a new section on censoring rules (Section 10.10) and deletion of censoring details from Section 9.5. Previous content of Section 10.10 moved to a new Section 10.11 • Additional instructions provided in Section 10.5.1 in case of missing AE start date, • Re-arrangement and slight modifications to the imputation rules for missing or incomplete case onset dates in Section 10.7.2 • Asymptomatic cases of SARS-CoV-2 infections added to the section on adjudication (Section 10.7.5) • Update of the section on “Event Dates, Follow-Up Time, Time to Event Calculation and Censoring” (Section 10.11, previously 10.10) to take into consideration the unblinding context • Addition of the type of confidence interval (Wald) derived on the hazard ratio in Section 12.8.1.4 • Addition of SMQ/CMQ in Section 10.5.7, reporting thereof (Section 12.6.1.1) and list of term (Appendix 3) • Addition of sensitivity analysis on Safety outputs to account for censoring rules in main analyses (Section 12.6.6) • Addition of reporting of selected solicited local and systemic AEs by Gender (Section 12.6.1.2)
2.0 / 29-Apr 2021	Finalization of Draft 1.1 without any further changes
3.0 (2.1) / 15-Jul-2021	Updates 
 • Overall: Harmonized nomenclature around alternate vaccine to read “alternate / licensed / authorized” • Overall: Changed naming of endpoints containing “through 1 year after second trial vaccination” to read “through EOT Visit”. • Section 8.2: 
 ○ Removed planned interim analysis. ○ Early immunogenicity delivery and related unblinding of designated CRO added. • Section 8.6 Added unblinding timepoint of designated CRO. • Section 9.4: Modified introductory sentence to allow for changes from protocol in the estimand table. • Section 9.5: Added that analyses using all randomized subjects will be based on vaccination “as randomized”.

	
 • Section 9.5.2 Added that Subjects who received an alternate / licensed / authorized vaccine prior to 15 days after the second vaccination will be excluded from IS. • Section 9.5.5: 
 ○ Reworded the EAS definition to make it clearer. ○ Added unblinding and alternate / licensed / authorized vaccine receipt. ○ Added use of adjudication data. • Section 9.5.6: Modified EASS definition to not exclude subjects after unblinding. • Section 10.6.1: Added serology status at baseline and serology status at Visit Day 43 definition. • Section 10.7.4: Corrected formula for Symptom onset \geq 15 days after second trial vaccination. • Section 10.11: Added date of alternate / licensed / authorized vaccine + 1 to the censoring date formula. • Section 10.12: Added section regarding age groups. • Section 11: 
 ○ Removed planned interim analysis. ○ Added possible ad-hoc analyses around early conditional approval in Europe. • Section 12.1: 
 ○ Screen failures were removed. ○ Description of tables was adapted to match the required outputs. ○ Summary of censored subjects was added. ○ Summary of stratification and treatment errors was added. • Section 12.2: Added combined (adjudication + EDC) serology status variable • Section 12.3: 
 ○ Adapted analysis description of medical/surgical history to match required analyses. ○ Added co-morbidities analysis. • Section 12.5: Added subject- and site-level for protocol deviations. • Section 12.6.1.1 Re-arranged solicited and unsolicited AE analysis descriptions to reflect the required analyses, added Section 12.6.1.3. • Section 12.7: Added that no "Total" summaries will be provided for immunogenicity. • Section 12.8.1.1: Added usage of adjudication data for serostatus at baseline and Visit Day 43. • Section 12.8.1.4: Added sensitivity analysis for one secondary endpoint. • Appendix 2: 
 ○ Removed Multisystem inflammatory syndrome in children from AESI list ○ Removed COVID-19 disease from AESI list

4.0 / 08 Apr 2022
	
 • Section 1.0: Updated signatories details • Section 6.0: Added info that main stakeholders are unblinded at time of SAP update • Section 6.1: Changes from protocol were updated

- Section 7.2.1: Secondary efficacy objective on asymptomatic cases was deleted.
- Section 7.2.2: Secondary immunogenicity objective on lot-to-lot consistency was deleted.
- Section 7.3: All exploratory objectives were deleted.
- Section 8.2: Added EOT wording for placebo subjects after study unblinding.
- Section 8.5.2: Adapted Sample information on primary immunogenicity objective to new analysis scope.
- Section 8.6: Updated unblinding information according to protocol 3.0 and study development.
- Section 9.1.2: Reduced timepoints for immunogenicity analyses to Days 1, 29 and 43.
- Section 9.2.1: Reduced secondary efficacy endpoints according to scope reduction in EOT delivery.
- Section 9.2.2: Reduced timepoints for immunogenicity analyses to Days 1, 29 and 43. Reduced secondary immunogenicity endpoints according to scope reduction in EOT delivery.
- Section 9.3: Deleted all exploratory endpoints.
- Section 9.4: Updated "Estimands" table to match study.
- Section 9.5.2: Updated IS definition to not exclude subjects who had received an AV prior to 15 days after 2nd vaccination.
- Section 9.5.4: Reduced PPI Set to 250 subjects.
- Section 9.5.6: Mentioned that EASS is not further applicable.
- Section 9.5.7: Updated and corrected Summary of Analysis Sets
- Section 10.5.5: Corrected AESI definition
- Section 10.5.8: Added Section defining overreported AEs.
- Section 10.6, and 10.6.1: Updated wording according to protocol v 3.0 and for clarity reasons
- Section 10.6.2.3 and 10.6.3: Deleted Sections on seroconversion to N protein antibodies and CMI.
- Section 10.7.1.1 and 10.7.2 and 10.7.5: Provided for a local instead of a central laboratory being used
- Section 10.10: Added unblinding column to censoring table.
- Section 10.11: Updated overview table to match analysis updates.
- Section 11.0: Updated IA info to match study development.
- Section 12.0 and 12.2 and 12.4.2 and 12.6.1.2: Updated to match study development and reduced EOT analysis.
- Section 12.6.1.4: Added section on repeats of AE analyses without censoring
- Section 12.6.7: Added section on adapting the safety analyses to the requirements of extensive unblinding
- Section 12.7 and 12.7.1: Reduced timepoints for immunogenicity analyses to Days 1, 29 and 43.
- Section 12.7.2 and 12.8.1.1 – 12.8.1.4: Adapted to account for reduced EOT analyses.
- Section 12.7.3 and 12.8.2: Deleted to account for endpoint deletion.

4.0 Purpose

The Statistical Analysis Plan (SAP) describes the statistical methods to be used during the reporting and analyses of data collected under CureVac AG Protocol CV-NCOV-005.

5.0 Scope

The SAP outlines the following:

- Trial Objectives
- Trial Design
- Trial Endpoints and Assessments
- Analysis Sets
- Conventions and Definitions
- Applicable Trial Definitions
- Statistical Methods

6.0 Introduction

The SAP describes the statistical methods to be used during the reporting and analyses of data collected under CureVac AG Protocol CV-NCOV-005.

The SAP should be read in conjunction with the trial protocol version 5.0 dated 22-Dec-2021 and Case Report Form (CRF) v4.0 dated 10-Jun-2021.

This SAP describes the statistical methods used for the final analysis. The SAP v1.0 is approved prior to the first relevant delivery¹. Changes following approval of the first version of the SAP are tracked in the SAP Change Log and the last final SAP version is approved prior to final database lock.

Each version of the SAP requires approval by the Sponsor.

It must be noted that all main stakeholders from the combined Sponsor and designated Contract Research Organization (CRO) (PRA/ICON) study team have been unblinded between approval of SAP versions 3.0 and 4.0. As a consequence, the SAP version 4.0 is created and approved by an unblinded authorship/approval team.

6.1 Changes from Protocol

- 1) Addition of sensitivity analysis on Safety outputs for Safety Interim Analysis (IA) to account for censoring rules in main analyses (Section 12.6.6)
- 2) Inclusion of Adverse Events (AEs) Related to Standardized and Customized Medical Dictionary for Regulatory Activities (MedDRA) Queries (CMQs)
- 3) The planned IA to obtain early conditional approval in Europe was removed.
- 4) An early immunogenicity delivery and related unblinding of PRA/ICON was added.
- 5) Update to analysis sets (Section 9.5) to account for unblinding and/or Authorized Vaccine (AV) application.
- 6) Protocol deviations are classified in site- and subject-level protocol deviations.
- 7) A sensitivity analysis on a secondary endpoint was added, according to what was done in the CV-NCOV-004 study.

¹ This was the safety delivery for the rolling submission when subjects randomized by (including) 11-Feb-2021 had reached 6 weeks post 2nd dose.

- 8) Multisystem inflammatory syndrome in children was removed from Adverse Event of Special Interest (AESI) list
- 9) The Efficacy Analysis Set (EAS) excludes subjects who were unblinded prior to 15 days after the second vaccination or received an AV prior to 15 days after the second vaccination
- 10) In the protocol synopsis the definition of the efficacy endpoint does no longer require the subject to be N negative. This is considered an erroneous deletion and is ignored.
- 11) "Non-serious intercurrent medical conditions that may affect the immune response to vaccination will also be collected throughout the trial." is taken out of the AESI definition.
- 12) The secondary immunogenicity endpoint lot to lot consistency is not to be analyzed.
- 13) From the secondary efficacy endpoint "Occurrence of first episodes of virologically-confirmed (RT-PCR positive) symptomatic cases of COVID-19 meeting the case definition for the efficacy analysis by severity (mild, moderate, severe and moderate to severe COVID-19)" only the mild cases are analyzed .
- 14) No repeat of any of the secondary efficacy analyses on the Safety Analysis Set (SAS) is done.
- 15) Protocol Section 10.3.7.1 requires the secondary efficacy analyses of prevention or reduction of asymptomatic infections as measured by seroconversion to the N protein to be performed, although this was deleted from all other sections in the protocol. This is considered an oversight and therefore this analysis is not performed.
- 16) The Vaccine Efficacy (VE) analysis of Burden of Disease (BoD) is not performed.
- 17) The sensitivity analysis by Kaplan-Meier (KM) curves for the time to first occurrence of virologically-confirmed COVID-19 case of any severity is not performed. No sensitivity analysis of this endpoint on the SAS is performed either.

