## 10.2 Populations for Analyses

### 10.2.1 Safety Analysis Set

The Safety Analysis Set (SAS) will include all subjects randomized in the trial who received at least 1 dose of any lot of CVnCoV or placebo vaccine.

The SAS will be the primary population for safety endpoints collected on all subjects (i.e. medically-attended AEs, AESI, AEs leading to vaccine withdrawal or trial discontinuation and SAEs) and a supportive population for efficacy endpoints.

For safety analyses on the SAS, subjects will be analyzed in the group of treatment they actually received (as “treated”).

For efficacy analyses on the SAS, subjects will be analyzed in the group of treatment to which they were randomized (as “randomized”) to follow the “intent to treat” principle.

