SV = mean BoD score in vaccinated group (pooled lots) / mean follow-up time (months) of evaluable subjects in the CVnCoV groups.

SP = mean BoD score in placebo group / mean follow-up time (months) of evaluable subjects in the Placebo group.

The 95% CI of the  $VE_{BoD}$  will be based on the normal distribution.

All efficacy endpoints will be analyzed descriptively without success criteria testing on the EAS.

A supportive analysis will be done on the SAS including all subjects whatever their serological status at baseline and considering all events occurring at any time after the first trial vaccination.

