9.5.5 Efficacy Analysis Set (EAS)

The EAS includes all subjects of the SAS who:

- Received both trial doses according to their randomization (two doses of the same lot of CVnCoV if randomized to that lot or two doses of placebo if randomized to placebo).
- Had not developed a virologically-confirmed case of COVID-19 before trial entry (based on exclusion criteria 1, see Trial Protocol)
- Had not developed a virologically-confirmed case of COVID-19 (definition in Section 10.7.2) or an asymptomatic case of SARS-CoV-2 (definition in Section 10.8) before 15 days after the second vaccination.
- Had not stopped the trial before 15 days after the second vaccination.
- Were SARS-CoV-2 naïve at baseline (Visit Day 1) and Visit Day 43 (based on seronegativity to N protein in the blood sample).
- Were not unblinded or in receipt of AV prior to 15 days after the second vaccination (See Section 10.10)

Where available the information assessed by the independent adjudication Committee of clinicians (Section 10.7.5) is used.

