# restricted to subjects naïve to SARS-CoV-2 N protein antibodies at baseline		

Table 4: Summary of Analysis Sets to be Used per Analysis - Efficacy Endpoints

Endpoint Type	Endpoint Short Description	Primary Analysis Set	Supportive Analysis Set
Secondary Efficacy Endpoint	First episodes of COVID-19 cases.	EAS	SAS#
	Severity assessment of first episodes of COVID-19 cases.	EAS	SAS#
	BoD Scores	EAS	SAS#
	Second episodes of COVID-19 cases	EAS	SAS
Exploratory Efficacy Endpoint	Second episodes of COVID-19 cases	EAS	SAS

#Including all subjects whatever their serological status at baseline and considering all events occurring at any time after the first trial vaccination.

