12.1 Subject Disposition

The number and percentage of subjects who prematurely withdraw from treatment, prematurely withdraw from the trial and a breakdown of the corresponding reasons for treatment withdrawal and early trial discontinuation is provided. Reasons for withdrawal are listed for subjects who prematurely withdraw from treatment or prematurely withdraw from the trial.

The number and percentage of subjects randomized and treated is presented with the number and percentage of subjects included in each analysis set. Reasons for exclusion from each analysis set are not tabulated, but are listed.

Subjects whose data is censored due to unblinding for AV treatment being available, are summarized for unblinding and / or AV use before dose 2 and after dose 2 for SAS and randomized subjects. A separate listing is provided indicating the date a subject was unblinded / received an AV. Subjects who have received an AV without being unblinded are also included in that listing.

The number and percentage of subjects who were not stratified correctly is presented along with the number of subjects who received an incorrect vaccine at first and/or second vaccination. The summary is done for all randomized subjects. Subjects are also listed accordingly.

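### SAP v4.0 cancels, without a stated reason, the supportive efficacy analysis from dose 1 on all vaccinated subjects that the protocol still requires

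*SAP*

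**What the plan says.** **Protocol v5.0.** Section 10.3.7.1 states: "A supportive analysis will be done on the SAS including all subjects whatever their serological status at baseline and considering all events" after the first trial vaccination. Table 6 names the SAS as supportive set for the any-severity and severity endpoints. Section 10.2.1 fixes the grouping on the intent-to-treat principle: "For efficacy analyses on the SAS, subjects will be analyzed in the group of treatment to which they were randomized". The protocol's time-to-event sensitivity analysis starts 15 days after dose 2, so the SAS analysis is the only planned efficacy analysis that starts at dose 1.

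**SAP v4.0, operative text.** Section 6.1 item 14: "No repeat of any of the secondary efficacy analyses on the Safety Analysis Set (SAS) is done". Item 17 adds: "No sensitivity analysis of this endpoint on the SAS is performed either". Sections 12.8.1.1 to 12.8.1.4 name only the EAS.

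**SAP v4.0, text that still assumes SAS efficacy analyses.** Table 4 (9.5.7) keeps the SAS as supportive set, with the footnote "Including all subjects whatever their serological status at baseline and considering all events occurring at any time after the first trial vaccination". Section 9.5 describes efficacy analyses on the SAS as treated, with an optional repeat as randomized. Section 10.6.1 keeps a rule for endpoints that count cases from the first vaccination.

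**EAS (SAP 9.5.5).** Subjects must have had both doses as randomized, no confirmed COVID-19 or asymptomatic infection before 15 days after dose 2, no earlier trial exit, and N-seronegativity at baseline and Day 43. The SAP adds: "Were not unblinded or in receipt of AV prior to 15 days after the second vaccination".

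**Disposition (SAP 12.1).** "Reasons for exclusion from each analysis set are not tabulated, but are listed".

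**The concern.** The protocol pairs a selected main set with a broader check. The EAS answers a question about fully vaccinated, still-naïve subjects. The SAS analysis asks whether the answer survives when everyone vaccinated is kept in the arm to which they were randomized and every case is counted.

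Without the second analysis, every VE figure comes from a set defined by events after randomisation, several of which the vaccine or its reactogenicity could influence: receiving dose 2, early infection, leaving the trial, asking to be unblinded. If these differ by arm, the EAS comparison can be distorted, and no second estimate would show it.

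The way the analysis was removed adds to the concern. SAP 6.1 items 10 and 15 explain why protocol text is set aside; item 14 does not. SAP 6.0 says that v4.0 was written and approved by an unblinded team. An unexplained removal in those circumstances should be justified or reversed. The leftover text in 9.5, 9.5.7 and 10.6.1 also leaves a programmer unsure what to run.

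**Working it through.** The documents give no efficacy sample size, case count or power, so there is no plan figure for efficacy to reproduce. The check traces the analysis sets and the case window, then sizes the window.

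**1. Required against planned**

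| Item | Protocol v5.0 | SAP v4.0 |
|---|---|---|
| Supportive SAS efficacy analysis | Required (10.3.7.1, Table 6) | Cancelled (6.1 items 14, 17); still in Table 4 |
| Grouping on the SAS | As randomized (10.2.1) | As treated, optional repeat as randomized (9.5) |
| Start of case counting | Dose 1 for the SAS analysis | Dose 2 + 15 days for all first-episode and burden-of-disease rows (Table 8) |
| Sets named in the methods | EAS and SAS | EAS only (12.8.1.1 to 12.8.1.4) |

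The second-episode row of Table 8 starts after a first primary case, so it does not capture early cases either.

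**2. Length of the excluded window.** Dose 2 is nominally on Day 29. Counting starts at Day 29 + 15 = Day 44. Days 1 to 43 are excluded: 43 days.

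**3. Share of follow-up**
- Planned schedule: 43/393 = 10.9%.
- If blinded follow-up after Day 43 averages 120, 60 or 30 days (assumption; the documents give no figure): 43/163 = 26.4%, 43/103 = 41.7%, 43/73 = 58.9%.

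**4. How far a from-dose-1 VE could differ (illustration).** Assume a constant placebo hazard, X days of total follow-up from dose 1 in both arms, later VE of 48.2% (the CV-NCOV-004 result in the protocol synopsis) and early VE between 0 and 48.2%. With w = 43/X:

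VE from dose 1 = w × VE(early) + (1 − w) × 48.2%

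| X (days) | w | Early VE = 0 | Early VE = 48.2% |
|---|---|---|---|
| 393 | 0.109 | 42.9% | 48.2% |
| 180 | 0.239 | 36.7% | 48.2% |
| 120 | 0.358 | 30.9% | 48.2% |
| 90 | 0.478 | 25.2% | 48.2% |

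This shows the effect of the time window alone. It is not an estimate of bias in the EAS result, because the two analyses answer different questions.

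**5. What remains visible by arm.** SAP 12.0 presents summaries by vaccine group by default.

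| EAS criterion | Tabulated elsewhere? |
|---|---|
| Set size | Yes, 12.1 |
| Both doses as randomized | Yes: doses given and reasons not given (12.4.1), wrong vaccine (12.1) |
| Trial exit | Withdrawals with reasons (12.1) |
| Unblinding or authorized vaccine (AV) | Before and after dose 2 (12.1), not split at Day 15 after dose 2 |
| N-serostatus at baseline and Day 43 | Yes, 12.2 |
| Infection before Day 15 after dose 2 | No |
| Exclusion reasons in one table | No; listed only |

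**The case against.** The strongest reply is that little depends on this analysis. Efficacy is secondary and descriptive with no success criteria. CV-NCOV-004 has already reported final efficacy. Protocol 9.4.2 calls efficacy in this trial inconclusive because approved vaccines were given at different times in all groups. Most EAS criteria are the protocol's own estimand, and item 14 leaves the main analysis untouched. The cancellation is disclosed, and SAP 12.0 says that the end-of-trial scope was reduced in agreement with the sponsor. The table list (Appendix 4) is held outside the SAP, so what was actually programmed cannot be confirmed. All of this stands and limits the weight of the point. None of it supplies the missing analysis or a reason for dropping it.

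Several stronger readings are tempting but not supported:

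- **That differential selection is hidden.** It is not: set sizes and most EAS criteria appear by arm in other tables. The gap is early infection and a single table of reasons.
- **That early cases are seen nowhere, or that disease enhancement goes unwatched.** SAP 12.0 lists collected data unless otherwise specified. Protocol 9.3.3 and SAP Appendix 2 treat COVID-19 as an adverse event of special interest (AESI), and AESIs are tabulated on the SAS (12.6.1.3). SAP 10.5 says that confirmed COVID-19 is not an adverse event, so whether it is counted there is unclear. Disease enhancement is assigned to the DSMB, which reviews cases by vaccine group (protocol 5.1, 7.3.2).
- **That most case-accrual time is lost.** That needs the 30-day assumption.
- **That the unblinded team removed the analysis because of results.** Nothing in the documents shows this.

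**Conclusion.** The point holds as a correctable defect. A protocol-required supportive analysis is cancelled without a reason, and the SAP contradicts itself about it. On the operative text, VE has no check outside a set selected after randomisation, and cases in the first 43 days reach no planned efficacy table.

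The window is certain on the nominal schedule; its share is not. It is 11% of planned follow-up. The 26% to 59% range depends entirely on assumed follow-up, although short blinded follow-up is plausible: SAP 12.6.7 refers to extensive data loss through censoring, and protocol 9.4.3 says that most subjects received an authorized vaccine.

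The restored analysis would be closer to the randomised comparison but not fully protected by it, because censoring at unblinding or authorized vaccination also depends on events after randomisation. The issue is how far a descriptive VE can be interpreted. It affects neither type I error nor the primary safety and immunogenicity objectives.

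**What to change.** 1. In SAP 6.1, delete item 14 and the last sentence of item 17.
2. In 12.8, apply the 12.8.1.1 VE method (cases, person-time, exact interval) to the SAS as randomized, from dose 1, regardless of serostatus, censored as in 10.10 and labelled supportive and descriptive. Table 8 has no row starting at the first vaccination, so add one.
3. Show cases by arm, separately before and from Day 15 after dose 2. The protocol does not ask for this split, but it makes the combined figure readable.
4. In 9.5, change efficacy on the SAS to as randomized. Reconcile 6.1, 9.5, 9.5.7, 10.6.1 and 12.8, and state whether COVID-19 is counted in the AESI tables (10.5 against Appendix 2 and protocol 9.3.3).
5. In 12.1, tabulate EAS exclusion reasons by arm.

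The cost is SAP wording, existing VE code rerun on another set (one or two tables), and one disposition table. The supportive VE will probably be lower than the EAS figure and less clean to interpret, since it mixes partial and full vaccination.
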